Adverse reaction (AR) is any harmful, unintended reaction to an investigational drug, regardless of the dose administered. In this case, there is a suspicion of a causal relationship between the investigational drug and the adverse event.

Serious adverse event (SAE) is any adverse event that, at any dose, results in death, threatens the life of the subject, makes hospitalization necessary or prolonged hospitalization, results in permanent or significant disability or disability, or results in a congenital anomaly or malformation. For the purposes of notification, suspected adverse events that are considered medically significant, even if they do not meet the above criteria, will also be treated as serious, including major medical events that require intervention to prevent one of the consequences described above from occurring. Likewise, all suspected transmission of an infectious agent through a drug will be reported as serious. Examples of these events include allergic bronchospasm requiring intensive treatment in an emergency department or at the individual's home, blood dyscrasia or seizures that do not require hospitalization, or the development of drug dependence or abuse.

Medical and scientific judgement should be used to decide whether other situations that have not resulted in the outcomes listed in the above definitions should be reported as SAGs.

A life-threatening term is defined as a situation where, in the opinion of the physician, the patient at the time of the adverse event or adverse reaction is at real risk of death.

Hospitalization or prolongation of a hospitalization is a criterion for considering an AA to be serious. Only admission in which the patient spends the night in the hospital should be considered as hospitalization. The following situations will not meet the AAG criteria:

- if hospitalization or prolongation of hospitalization is necessary to perform a procedure required by the protocol (for example, if day or night visits will be made for biopsies or surgeries required by the protocol).
- if hospitalization or prolongation of hospitalization is part of the facility's routine procedure (e.g., removal of a stent after surgery)
- in case of scheduled hospitalization for a pre-existing process that has not worsened (e.g. scheduled hospitalization for the implantation of a knee prosthesis for a previous osteoarthritis process)

Grade IV laboratory alterations will be considered AAG.

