DO NOT confuse the concept of "serious" with "severe" which refers to the intensity of the adverse event or adverse reaction.

Unexpected serious adverse reaction (RAGI) is a serious adverse reaction whose nature or severity does not correspond to the information regarding the product (for example, the investigator's manual in the case of an investigational medicinal product not authorised for marketing or the product label in the case of an authorised medicinal product).

b) Imputability criteria.

The causal relationship between the investigational product and the occurrence of AA/AAG shall be established on the basis of clinical judgment. To this end, other causes will be considered and studied, such as the natural history of the underlying diseases, concomitant treatment, other risk factors and the temporal relationship of the event with the investigational product. In addition, the technical data sheet of the products will be consulted.

In order to analyse the possible cause-effect relationship, the temporal relationship between the administration of the drug and the AA, possible alternative causes, the evolution (complete remission,

partial recovery, death, sequelae, persistence), persistence or not after the suspension of administration, reappearance with the readministration of the product or the prior knowledge of said event coinciding with the known or expected response pattern of the drug under study will be considered.

The causal relationship of an AA with the medication under study will be established according to the following definitions:

Unlikely relationship: The adverse event does not occur after a plausible chronological sequence related to the administration of the product under study and/or is reasonably explainable by other factors, such as the patient's clinical status or other concomitant therapeutic, toxic, or environmental interventions. In addition, it does not match the known or expected response pattern of the drug.

Possible relationship: the adverse event occurs after a plausible chronological sequence related to the administration of the product under study, but can also be explained by the patient's clinical status or other concomitant therapeutic, toxic, or environmental interventions. It also matches the known or expected response pattern of the drug.

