Probable relationship: The adverse event occurs after a plausible chronological sequence related to the administration of the product under study, cannot be reasonably explained by the patient's clinical status or other concomitant therapeutic, toxic, or environmental interventions, and after withdrawal or reduction of the dose of the suspect drug the event follows a logical clinical sequence. It also matches the known or expected response pattern of the drug.

Very likely relationship: the adverse event occurs after a plausible chronological sequence related to the administration of the product under study, cannot be reasonably explained by the clinical status of the patient or other concomitant therapeutic, toxic or environmental interventions, after withdrawal or reduction of the dose of the suspect drug the event follows a logical clinical sequence and it is necessary that after the readministration of the suspicious drug the adverse event reappears. It also matches the known or expected response pattern of the drug.

Unrelated: Adverse event clearly due to causes unrelated to the medication under study and the criteria for another causal relationship are not met.

Non-assessable relationship: any notification that suggests an adverse effect, which cannot be judged because the information is insufficient or contradictory and which cannot be supplemented or verified.

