11.3 Analysis

In this open study, all variables will be tabulated. Quantitative variables will be described by the number of available and omitted observations, the mean, the median, the standard deviation, the interval (minimum and maximum) and the first and third quartiles. Of the qualitative variables, the frequency and percentage will be presented. Omitted values will be tabulated with their frequency, but will not be included in the calculation of the percentages.

The primary endpoint will be assessed with a bilateral CI of 95% around the observed proportion of SVR. The analysis of the primary endpoint in SVR will be carried out in two ways. Patients who withdrew from the study within the first four weeks will be included in the main analysis, which will be counted as SVR failures. As a secondary analysis, an SVR analysis will also be performed, but restricted to patients who have not withdrawn from the study in the bitherapy period in the first four weeks. In both analyses, patients in whom SVR data are lacking due to premature withdrawal from the study at any time after the initial bitherapy period of the first four weeks will be included and counted as SVR failures.

Inferential analysis of boceprevir efficacy will be assessed by SVR at week 24 and the 95% confidence interval. A similar analysis will be applied to evaluate the secondary variables. For continuous quantitative variables, the mean or median and the 95% confidence interval or the interquartile interval shall be calculated.

Descriptive analyses of treatment-occurring adverse events and treatment-occurring adverse events that are possibly or likely related to the study drug will be performed. With regard to the safety assessment in the AEs, the 95% CI of the percentage of grade 3 or higher adverse events and other serious adverse events reported by the centres shall be provided. The highest grade episode per person over time will be used. Descriptive tables will be provided summarizing the events and the number of people who have presented the events by grade.

Variations in HIV-1 viral load or RNA and CD4+ T cell count at each post-enrollment visit will be summarized. The rates and reasons for premature discontinuation of treatment, including HCV treatment failures, will be summarized.

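### The causality scale in section 10.1 b) makes a match to the drug's known or expected pattern a condition of relatedness, so a reaction new to the drug has no related category and its place in the related-event analysis is undefined

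*Combined protocol and SAP*

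**What the plan says.** Section 10.1 b) opens with clinical judgment and lists factors to consider, prior knowledge of the event among them. It then says: "The causal relationship of an AA with the medication under study will be established according to the following definitions". The categories that follow are:

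- *Possible*: plausible timing, but the event can also be explained by other factors.
- *Probable*: plausible timing, no other reasonable explanation, and a logical course after withdrawal or dose reduction.
- *Very likely*: as *probable*, and "it is necessary that after the readministration of the suspicious drug the adverse event reappears".
- *Unlikely*: implausible timing and/or a reasonable other explanation. It adds: "In addition, it does not match the known or expected response pattern of the drug".
- *Unrelated*: clearly due to another cause.
- *Non-assessable*: a report "which cannot be judged because the information is insufficient or contradictory and which cannot be supplemented or verified".

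*Possible*, *probable* and *very likely* each end: "It also matches the known or expected response pattern of the drug".

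Two other provisions depend on the outcome. Section 11.3 plans descriptive analyses of "treatment-occurring adverse events that are possibly or likely related to the study drug will be performed". Section 10.1 says that a RAGI "is a serious adverse reaction whose nature or severity does not correspond to the information regarding the product". Of an adverse reaction in general it says: "In this case, there is a suspicion of a causal relationship between the investigational drug and the adverse event".

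**The concern.** Whether a drug caused an event and whether the event was already known for that drug are separate questions. The scale merges them, because being known or expected is a condition of every related category. The RAGI definition needs them apart: a RAGI must be a suspected reaction and must also depart from the product information.

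Safety is part of the primary objective (sections 1.10.1 and 5). The study is single-arm (section 8.1), so no concurrent control group shows which rows of an all-event table exceed background. Individual attribution therefore carries more of the safety interpretation than it would in a randomised trial. If the definitions are followed, the related-event analysis leaves out reactions new to boceprevir. If some investigators set them aside, the count varies by site.

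**Working it through.** The plan gives no figure on this point, so the check is a logical one. Describe each event by five yes/no features taken from the definitions in section 10.1 b): plausible timing, another reasonable explanation, improvement on withdrawal or reduction, reappearance on re-administration, and match to the known or expected pattern. That gives 2^5 = 32 formal profiles, of which 16 do not match the pattern. A few are clinically odd, such as reappearance without improvement; they are kept so that the count is complete.

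**Current text, the 16 non-matching profiles**

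| Timing plausible | Other explanation | Profiles | Category |
|---|---|---|---|
| No | Yes or no | 8 | *Unlikely* |
| Yes | Yes | 4 | *Unlikely* |
| Yes | No | 4 | None of *unlikely*, *possible*, *probable*, *very likely* |

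Related: 0 of 16. *Unlikely*: 8 + 4 = 12. No category: 4.

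The last row includes the profile with both improvement on withdrawal and reappearance on re-administration, the strongest evidence the scale recognises. *Unrelated* does not take these four, because it needs a clear other cause. *Non-assessable* does not take them either, because it needs insufficient or contradictory information.

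**RAGI definition.** An event must be a suspected reaction and also fall outside the product information in nature or severity. A known reaction of unexpected severity can meet both conditions. A reaction of a new nature can meet both only if the known or expected pattern is read more widely than the product information.

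**Does simple deletion work?** Suppose the pattern sentence is removed from the three related categories and its negative from *unlikely*. For a plausibly timed event with another explanation, that sentence is all that separates *possible* from *unlikely*. With timing and other explanation both fixed at yes, three features remain free, so 2^3 = 8 of the 32 profiles would meet both categories. Four of those match the known pattern and are plainly *possible* today. Under the current text no profile meets both *unlikely* and a related category. Simple deletion therefore damages the scale.

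**Does a narrower change work?** Remove the sentence from *probable* and *very likely* only. Extend *possible* to plausibly timed events without another explanation that do not meet the withdrawal criterion. Leave *unlikely* as it is. The 16 non-matching profiles then fall as follows: 12 *unlikely*, 2 *possible*, 2 *probable* (1 of them also *very likely*), none without a category. Related: 2 + 2 = 4 of 16. Profiles meeting both *unlikely* and a related category: 0 of 32.

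**The case against.** The strongest reply is that little is lost. Section 11.3 calls the related-event analysis descriptive, and its intervals for grade 3 or higher and serious events do not depend on causality. It also analyses all adverse events whether or not related. Section 10.2 sends every serious event to the trials unit regardless of relatedness. All of this stands, and it limits the point to attribution.

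A second reply is that clinical judgment governs and that pattern match is only one of the listed considerations. This softens practice, but the section then says that the definitions establish the relationship. Following them excludes new reactions, and overriding them makes the count depend on the site.

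A third reply is that the drug is well described: section 10.3 cites nearly 1,500 treated patients, and section 4 reports co-infection results similar to those in monoinfection. This also narrows the point. The condition concerns the drug's pattern, not the population's, so a known boceprevir reaction that appears in co-infected patients, or is more frequent in them, still matches.

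Three stronger readings are tempting and are not supported:

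- **That a new toxicity would be reported as 0 of 128 in the related-event table.** An event without a category is indeterminate, not unrelated. Section 10.1 a) requires a relationship to be recorded for each event, so an investigator must choose something, and the documents do not say what.
- **That new toxicities would be hidden.** They remain in the all-event tables and, if serious, are notified.
- **That the RAGI definition is emptied.** Reactions of unexpected severity still qualify, and the known or expected pattern may be read more broadly than the product information.

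**Conclusion.** The point holds as a defect of definition, worth correcting and modest in consequence. All 3 related categories require the pattern match. As a result 0 of 16 non-matching profiles can be rated related, and 4 of 16 have no category. These are counts of logical profiles, not of patients or expected events. The documents give no rate for a new reaction and no rule for coding an event without a category, so no numerical effect on the safety results can be derived. The efficacy analysis is not touched.

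The conclusion assumes that the definitions are applied as written and that the known or expected pattern means roughly what is already described for the drug. A wider reading that includes pharmacologically anticipated effects would close the gap for those effects only.

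**What to change.** 1. In section 10.1 b), delete the pattern sentence from *probable* and *very likely*. Both already require that there be no other reasonable explanation, so neither can overlap with *unlikely*.
2. Redefine *possible* as plausible timing and either (a) also explainable by other factors and matching the known or expected pattern, as now, or (b) not reasonably explainable by other factors, whatever the pattern, when the withdrawal criterion for *probable* is not met or cannot be tested.
3. Leave *unlikely* unchanged, so that it stays separate from *possible*. A non-matching event that has another explanation will still be rated *unlikely*.
4. Judge expectedness separately, with one yes/no eCRF item on consistency with the product information, and use that item in the RAGI definition.
5. In section 11.3, define possibly or likely related as *possible*, *probable* or *very likely*, and split that analysis into expected and unexpected events.

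The cost is protocol wording, one eCRF field and one table split, with no extra patients, visits or samples. Slightly more events will be labelled related, including some known reactions without another explanation that have no category now because the withdrawal criterion is not met.

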10.2. Notification

The investigator or designee **must notify all AAGs, regardless of whether or not they are considered drug-related or planned**, to the CTU manager. [name] ([contact]) [contact] [name] and [contact] in order to notify local and national health authorities **within one working day of becoming aware of the event**, so that the contact of the designated promoter can prepare the corresponding written report. AAGs occurring will be reported at any time from the subject's inclusion in the study and up to 30 days after the study has been completed or discontinued. In the specific case of selection failure, the AAGs will be recorded from the moment the consent is signed until the subject is considered a selection failure.

Regardless of the classification of adverse effects, the Investigator must collect all the AEs in the corresponding section of the study data collection notebook (CRD) and fill in all the information pertaining to them.

The sponsor must notify in an EXPEDITIOUS manner all relevant SAFETY INFORMATION, i.e. that could modify the risk/benefit ratio of the investigational medicinal product, or determine changes in its administration schedule or in the conduct of the trial, for example:

- a qualitative change or an increase in the percentage of occurrence of expected RAGs, which is considered clinically important.
- RAGIs that occur after the completion of a clinical trial and that are notified by the investigator to the sponsor.
- New developments related to the conduct of the trial or the development of the investigational medicinal product and likely to affect the safety of the subjects, such as:
 - Serious adverse events that may be associated with the trial procedures and may modify the conduct of the trial
 - A significant risk to subjects such as the lack of efficacy of an investigational drug used for the treatment of a life-threatening disease.
 - Important new safety findings from new animal studies (such as cardiogenicity).
 - Any premature termination or temporary halt of a clinical trial with the same investigational medicinal product for safety reasons, carried out in another country and by the same sponsor.
 - GRAs related only to an MNI that are considered relevant as they are not subject to RAGI's general rules of expedited reporting of individual cases.
- Any recommendations from the data monitoring committee, which are relevant to the safety of the subjects.

This information must be notified as soon as possible and no later than 15 days after the promoter has become aware of it. In addition, if additional information that is relevant is obtained, it must be notified as quickly as possible.

10.3 Evaluation of toxicity parameters

The classification system for drug toxicity is set out in the DAIDS Table for Grading the Intensity of Adverse Events in Adults and Children, which can be found on the DAIDS RSC website: <http://rsc.techres.com/safetyandpharmacovigilance/>.

Treatment of PEG-IFN Side Effects

Side effects of PEG-IFN usually include flu-like symptoms such as myalgia, arthralgias, headache, chills, low-grade fever, nausea, vomiting, and tiredness, as well as erythema, pain, and edema at the injection site. Less common are side effects of the central nervous system (CNS), such as depression, insomnia, anxiety, and irritability. Abnormalities of thyroid function have been described, as well as neutropenia, thrombocytopenia, and alopecia. The decrease in neutrophil and platelet count is usually dose-dependent and usually reaches nadir by week 4. Reductions in the total number of white blood cells may also occur, although usually not below normal levels. In week 2, dose-related decreases have been observed for other analytical parameters, such as albumin, globulin, total proteins, potassium and calcium; however, most parameters normalize by week 4 of treatment. Inflammation at the injection site occurs intermittently throughout treatment, but usually does not limit it. In general, all these effects are reversed by decreasing or interrupting the dose; patients cannot continue to take RBV and BOC if PEG-IFN is permanently discontinued.

Treatment of IFN-associated neutropenia

Patients who develop neutropenia during treatment may receive G-CSF (not provided by the study) at the discretion of the center investigator.

Table 1. Treatment of toxicity: neutropenia

Parameter	Downward dose adjustment of PEG-IFN
RAN (cells/mm ³)	
Grade 1 (1,000- 1,300)	None

Grade 2 (750999)	No dose adjustment is necessary; G-CSF at the discretion of the centre's researcher
Grade 3 (500749)	Immediately reduce the dose by UN* one level and administer G-CSF at the discretion of the center investigator. If neutropenia disappears, the dose may be increased at the discretion of the center investigator.
Grade 4 (<500)	Study weeks 1 and 2: defer or discontinue administration until grade 2 is reached, then resume administration with dose reduction of DOS* levels. Study weeks 3 to 48: defer or discontinue administration until grade 2 is reached, then resume administration with a dose reduction of ONE level. Administer G-CSF at the discretion of the centre's investigator. If neutropenia disappears, the dose may be increased at the discretion of the center investigator.

* The dose reduction levels of PEG-IFN are indicated in the label.

Treatment of IFN-associated thrombocytopenia

Table 2. Treatment of toxicity: decreased platelet count

Platelet count (cells/mm3)	MEASURE
Grade 2 (50,000-99,999)	No
Grade 3 (25,000-49,999)	Halving the dose of interferon
Grade 4 (<25,000)	Suspend the PEG-IFN definitively.

* The dose reduction levels of PEG-IFN are indicated in the label.

Dose reduction of PEG-IFN

Dose reductions should be uniform between participating centers and patients. For this purpose, the following reductions shall be used:

Table 3. Guidelines for Recommended Dose Reduction of PEG-IFN 1.5 µg/kg

		Reduction of one level (decrease to 1.0 µg/kg)			Two-level reduction (decrease to 0.5 µg/kg)		
		Volume			Volume		
Weight at Sit Up*		Pen Size	Injection (ml)	Dosage (µg)	Pen Size	Injection (ml)	Dosage (µg)
40 to 50 kg	88 to 110 lbs	Redipen 50	0,45	45	Redipen 50	0,30	30
>50 to 60 kg	>110 to 132 lbs	Redipen 80	0,35	56	Redipen 50	0,30	30
>60 to 65 kg	>132 to 143 lbs	Redipen 80	0,40	64	Redipen 50	0,35	35
>65 to 75 kg	>143 to 165 lbs	Redipen 80	0,45	72	Redipen 50	0,35	35
>75 to 80 kg	>165 to 176 lbs	Redipen 80	0,5	80	Redipen 50	0,40	40
>80 to 85 kg	>176 to 187 lbs	Redipen 120	0,35	84	Redipen 50	0,40	40

>85 to 95 kg	>187 to 209 lbs	Redipen 120	0,40	96	Redipen 50	0,50	50
>95 to 105 kg	>209 to 231 lbs	Redipen 150	0,35	105	Redipen 50	0,50	50
>105 to 125 kg	>231 to 275 lbs	Redipen 150	0,35	105	Redipen 50	0,50	50

* Use the usual rounding methods: values between 0.1 and 0.4 kg should be rounded down and those between 0.5 and 0.9 kg should be rounded up.

Missed or deferred doses of PEG-IFN

If a dose of PEG-IFN is delayed but is finally administered, the following guidelines are recommended for the following scheduled doses:

- Dose delay of 1 or 2 days: administer on the usual day of administration of the week (for example, if Monday is the usual day of administration and the dose is delayed to Wednesday, the next dose will be administered as usual, on Monday).
- Dose delay of 3 to 5 days: Giving subsequent doses every 5 to 6 days until the patient gets back to their original schedule (for example, if Monday is the usual day of administration and the dose is delayed until Saturday, the next dose will be given on Thursday, the next dose on Tuesday, and the next dose on Monday).
- 6-day dose delay: discontinue that week's dose and continue with the usual schedule the following week (e.g. if Monday is the usual day of administration but the dose is delayed until the following Sunday, the dose is considered to have been interrupted and the next injection will coincide with the following week's dose, on Monday).
- Dose delay of 7 or more days: The investigator may resume administration of the study drug at any time up to 28 days after the last dose and, if necessary, administer the dose every 5 or 6 days until the weekly dose is received on the patient's usual scheduled day.

Treating the Side Effects of RBV

The most common AA in RBV treatment is anemia, which may be due to hemolysis or decreased release of red blood cells from the bone marrow. Anemia usually appears 1 to 2 weeks after you start receiving RBV and usually goes away within 4 to 8 weeks of withdrawal or reduction of the drug's dose. In patients with anemia secondary to RBV-induced hemolysis, an elevation of indirect bilirubin is common. BOC may increase the incidence or severity of anemia. In case of anaemia during treatment with BOC and RBV, the dose adjustment of RBV, as described below, takes precedence over BOC.

NOTE: A serious side effect of RBV is its teratogenicity; therefore, it is recommended not to administer RBV to pregnant or breastfeeding women and to men whose partner is pregnant. Women who become pregnant during the study will be required to discontinue study treatment and undergo withdrawal assessments.

The dose of RBV in this study will depend on weight at study entry (see section 5). The following table shows the recommendations for dose reduction in case of anemia. The administration of epoetin (EPO) will be at the discretion of the centre's researcher. If the administration of RBV is temporarily or permanently stopped, patients may continue to receive PEG-IFN and BOC.

Board. Recommended RBV dose reduction in anaemia

	Starting dose	Measure
--	---------------	---------

Hemoglobin <10 g/dL, ≥8.0 g/dL.	1,400 mg/day 1,200 mg/day	Decrease RBV to 1,000 mg/day
	1,000 mg/day	Decrease RBV to 800 mg/day
	800 mg/day	Decrease RBV to 600 mg/day
	600 mg/day	Decrease RBV to 400 mg/day (Initiate treatment with EPO at the discretion of the center's investigator)
Hemoglobin <8.0 g/dl	All doses	Temporarily discontinue the RBV
Symptomatic decrease in haemoglobin will be treated at the discretion of the centre's investigator.		

Reintroduction of RBV

In the event that RBV is temporarily stopped due to anaemia, haemoglobin values should be checked again after two weeks and then at two-week intervals until stabilised. If hemoglobin returns to an acceptable level, RBV should be reintroduced at doses of 600 mg/day (with a regimen of 200 mg in the morning and 400 mg in the evening). The dose may be increased by 200 mg/day every two weeks until the initial dose is reached.

Treatment of anemia with EPO is recommended, but this is not provided in the study. On the other hand, it is not advisable to administer EPO with hemoglobin values ≥10 g/dl. If necessary, at the discretion of the centre investigator, the dose of RBV may be reduced by a haemoglobin value ≥10 g/dl.

Increasing the dose of RBV

Once haemoglobin has returned to an acceptable level, patients who have had their RBV dose reduced without discontinuing their administration may, at the discretion of the centre investigator, increase the dose by 200 mg/day every two weeks until the initial dose is reached.

Missed doses: If a patient misses a dose of RBV, they should take it as soon as possible, along with food, during the same day. If a full day has passed, you should skip the missed dose and continue with the normal schedule of administration. In no case should the dose be doubled to "compensate" for the missed dose.

Treatment of Adverse Events Related to PEG-IFN alfa-2a and Ribavirin (PEGASYS™ PCR)

Dose adjustment in case of adverse reaction

	Reduce ribavirin to 600 mg	Suspend ribavirin	Reduce Pegasys to 135/90/45 micrograms	Suspend Pegasys	Suspended r la combination
Absolute neutrophil count			<750/mm3	<500/mm3	
Platelet count			<50,000/mm3 >25,000/mm3		<25,000/mm3

Hemoglobin - absence of heart disease	<10 g/dl , and ≥ 8.5 g/dl	<8.5 g/dl			
Hemoglobin - stable heart disease	Decrease ≥ 2 g/dL for any 4 weeks	< 12 g/dL despite 4 weeks at a reduced dose			

Treating BOC Side Effects

The safety profile represented by nearly 1,500 patients treated with the combination of boceprevir with peginterferon alfa-2b and ribavirin is derived from pooled safety data from two clinical trials in treatment-naïve patients and one clinical trial in treatment-failed patients.

The most frequently reported adverse events in the BOC/PEG/RVB groups were largely the reflection of events that are associated with the treatment spine (PEG/RBV).

The most frequent adverse reactions were fatigue, anemia, nausea, headache and dysgeusia. Only two adverse events, anaemia and dysgeusia, are 20% more common in boceprevir-containing treatments and will be discussed as events of particular interest.

Boceprevir monotherapy did not cause a decrease in hemoglobin in either the animal studies or a phase I monotherapy study. In healthy adult males who received boceprevir for up to 57 days, no effects on red blood cell formation, survival, and destruction or on markers of anaemia were detected. However, boceprevir added to PEG and RVB therapy results in a gradual decrease in hemoglobin of approximately 1 g/dL.

Treatment of anemia in patients receiving boceprevir polytherapy is identical to that of anemia in patients treated with peginterferon plus ribavirin. The incidence of discontinuation of treatment due to anemia is just as low, close to 1%, both in the control group with PEGIFN plus RBV and in the experimental groups treated with boceprevir.

Anemia in patients treated with boceprevir is transient, as baseline hemoglobin values recover after treatment.

Based on the above data, BOC is usually well tolerated and has an AA profile similar to that of the standard of care (PEG-IFN + RBV) with the exception of dysgeusia, which is more common in patients treated with BOC. The anemia appears to be mainly due to exposure to RBV.

Rules for processing

The dose of BOC cannot be reduced in the study.

Anaemia should be treated initially by reducing the dose of ribavirin and an erythropoiesis stimulant whenever available and appropriate. For dysgeusia, attempts will be made to reduce symptoms (e.g., pills, plastic cutlery, etc.). Treatment of headache and nausea should also be symptomatic. **Grade 1 and 2 AEs require close follow-up but no change in treatment.**

All grade 3 toxicities will be treated by the facility investigator as appropriate. Any grade 4 toxicity that, in the opinion of the centre's investigator, is directly related to BOC, will be treated with the permanent suspension of the latter.

In case of intolerance to the BOC, its administration will be suspended; The dose cannot be reduced. If BOC is temporarily or permanently stopped, patients may continue to receive PEG-IFN and RVB.

NOTE: EPO with hemoglobin values greater than or equal to 10 g/dl is not recommended.

